# 9.5.4.2 Reporting of Pregnancy and Exposure to Study Drug Through Breastfeeding

Any pregnancy in a female subject (or partner of a male subject) in which the estimated date of conception is either before the last visit or within 30 days of last study treatment, or any exposure to study drug through breastfeeding during study treatment or within 30 days of last study treatment, must be reported.

If an adverse outcome of a pregnancy is suspected to be related to study drug exposure, this should be reported regardless of the length of time that has passed since the exposure to study treatment.

A congenital anomaly, death during perinatal period, an induced abortion, or a spontaneous abortion are considered to be an SAE and should be reported in the same time frame and in the same format as all other SAEs (see Reporting of Serious Adverse Events [Section 9.5.4.1]).

Pregnancies or exposure to study drug through breastfeeding must be reported by fax or email as soon as possible but no later than 1 business day from the date the investigator becomes aware of the pregnancy. The contact information for the reporting of pregnancies and exposure to study drug through breastfeeding is provided in the Investigator Study File. The Pregnancy Report Form must be used for reporting. All pregnancies must be followed to outcome. The outcome of the pregnancy must be reported as soon as possible but no later than 1 business day from the date the investigator becomes aware of the outcome.

A subject who becomes pregnant must be withdrawn from the study. A subject who becomes pregnant may remain in the study if the investigator judges that the potential benefit to the subject outweighs any potential risk to the subject or the fetus and the subject gives informed consent for the further participation.

Eisai Confidential Page 96 of 138

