## 5 ETHICS

## 5.1 Institutional Review Boards/Independent Ethics Committees

The protocol, informed consent form (ICF), and appropriate related documents must be reviewed and approved by an Institutional Review Board (IRB) or Independent Ethics Committee (IEC) constituted and functioning in accordance with ICH E6 (Good Clinical Practice), Section 3, and any local regulations. Any protocol amendment or revision to the ICF will be resubmitted to the IRB/IEC for review and approval, except for changes involving only logistical or administrative aspects of the study (eg, change in clinical research associate [CRA], change of telephone number[s]). Documentation of IRB/IEC compliance with the ICH E6 and any local regulations regarding constitution and review conduct will be provided to the sponsor.

A signed letter of study approval from the IRB/IEC chairman must be sent to the principal investigator (or if regionally required, the head of the medical institution) with a copy to the sponsor before study start and the release of any study drug to the site by the sponsor or its designee (ICH E6, Section 4.4). If the IRB/IEC decides to suspend or terminate the study, the investigator (or if regionally required, the head of the medical institution) will immediately send the notice of study suspension or termination by the IRB/IEC to the sponsor.

Study progress is to be reported to IRB/IECs annually (or as required) by the investigator or sponsor, depending on local regulatory obligations. If the investigator is required to report to the IRB/IEC, he/she will forward a copy to the sponsor at the time of each periodic report. The investigator(s) or the sponsor will submit, depending on local regulations, periodic reports and inform the IRB/IEC (or if regionally required, the investigator and the relevant IRB via the head of the medical institution) of any reportable adverse events (AEs) per ICH guidelines and local IRB/IEC standards of practice. Upon completion of the study, the investigator will provide the IRB/IEC with a brief report of the outcome of the study, if required.

At the end of the study, the sponsor should notify the IRB/IEC and Competent Authority (CA) within 90 days. The definition of the end of the study is the date of the data cutoff for the final analysis or last subject/last visit, including discontinuation from the study for any reason, whichever occurs later. The sponsor should also provide the IRB/IEC with a summary of the study's outcome.

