#### 9.1.3.3 Extension Phase

In the Extension Phase, subjects who are receiving study drug at the end of the Treatment Phase will continue to receive drug treatment at the same dose and according to the Dosing Schedule described in Section 9.4.1.1.

In the **Treatment** and **Extension phases**, subjects will undergo disease assessments every 6 weeks in the case of solid tumors and 12 weeks in the case of lymphomas, and will discontinue study drug at the time of confirmed disease progression (per iRECIST or LYRIC), disappearance or nonavailability of any injectable lesions, development of unacceptable toxicity, subject request, withdrawal of consent, termination of the study program, pregnancy, or investigator decision.

An off-treatment assessment should occur within 30 days after the final dose of study treatment.

Subjects who are continuing to derive clinical benefit in the view of the investigator at the time of study termination by the sponsor, can continue to be treated with E7766 after discussion with the sponsors.

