- 11. Any history of a medical condition or a concomitant medical condition that, in the opinion of the investigator, would compromise the subject's ability to safely complete the study.
- 12. Females who are breastfeeding or pregnant at Screening or Baseline (as documented by a positive beta-human chorionic gonadotropin [β-hCG] (or human chorionic gonadotropin [hCG]) test with a minimum sensitivity of 25 IU/L or equivalent units of β-hCG [or hCG]). A separate baseline assessment is required if a negative screening pregnancy test was obtained more than 72 hours before the first dose of study drug.
- 13. Females of childbearing potential must not have had unprotected sexual intercourse within 30 days before study entry and must agree to use a highly effective method of contraception (total abstinence [if it is their preferred and usual lifestyle], a contraceptive implant, an oral contraceptive, or have a vasectomized partner with confirmed azoospermia) throughout the entire study period and for 180 days after study drug discontinuation. For sites outside of the EU, it is permissible that if a highly effective method of contraception is not appropriate or acceptable to the subject, then the subject must agree to use a medically acceptable method of contraception, ie, double barrier methods of contraception such as condom plus diaphragm or cervical/vault cap with spermicide. If currently abstinent, the subject must agree to use a highly effective method as described above if she becomes sexually active during the study period or for 180 days after study drug discontinuation. Females who are using hormonal contraceptives must have been on a stable dose of the same hormonal contraceptive product for at least 28 days before dosing and must continue to use the same contraceptive during the study and for 180 days after study drug discontinuation.

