- 14. Male subjects who are partners of women of childbearing potential must use a condom and spermicide and their female partners if of childbearing potential must use a highly effective method of contraception (see methods described above in Exclusion Criterion #13) beginning at least 1 menstrual cycle prior to starting study drug(s), throughout the entire study period, and for 180 days after the last dose of study drug, unless the male subjects are totally sexually abstinent or have undergone a successful vasectomy with confirmed azoospermia or unless the female partners have been sterilized surgically or are otherwise proven sterile. No sperm donation is allowed during the study period or for 180 days after study drug discontinuation.

Eisai Confidential Page 63 of 138

- Known hypersensitivity to E7766 or any of the excipients or prior therapy with E7766 or any other STING agonist.
- 16. Use of illegal recreational drugs.
- 17. Currently enrolled in another clinical study or used any investigational drug or device within 28 days preceding informed consent.

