### 9.5.1.5.2 Serious Adverse Events and Events Associated With Special Situations

An SAE is any untoward medical occurrence that at any dose:

- Results in death
- Is life-threatening (ie, the subject was at immediate risk of death from the adverse event as it occurred; this does not include an event that, had it occurred in a more severe form or was allowed to continue, might have caused death)
- Requires inpatient hospitalization or prolongation of existing hospitalization
- Results in persistent or significant disability/incapacity
- Is a congenital anomaly/birth defect (in the child of a subject who was exposed to the study drug)

Other important medical events that may not be immediately life-threatening or result in death or hospitalization but, when based on appropriate medical judgment, may jeopardize the subject or may require intervention to prevent one of the outcomes in the definition of SAE listed above should also be considered SAEs. Medical and scientific judgment should be exercised in deciding whether expedited reporting is appropriate in such situations.

In addition to the above, events associated with special situations include pregnancy or exposure to study drug through breastfeeding; AEs associated with study drug overdose, misuse, abuse, or medication error. These events associated with special situations are to be captured using the SAE procedures but are to be considered as SAEs only if they meet one of the above criteria. All AEs associated with special situations are to be reported on the CRF whether or not they meet the criteria for SAEs.

All SAEs must be followed to resolution or, if resolution is unlikely, to stabilization.

The following hospitalizations are not considered to be SAEs because there is no "adverse event" (ie, there is no untoward medical occurrence) associated with the hospitalization:

- Hospitalizations for respite care
- Planned hospitalizations required by the protocol
- Hospitalization planned before informed consent (where the condition requiring the hospitalization has not changed after study drug administration)
- Hospitalization for administration of study drug or insertion of access for administration of study drug
- Hospitalization for routine maintenance of a device (eg, battery replacement) that was in place before study entry

Eisai Confidential Page 84 of 138

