# 9.5.3 Appropriateness of Measurements

All clinical assessments are standard measurements commonly used in studies of oncology studies.

The safety assessments to be performed in this study, including hematology analyses, blood chemistry tests, urinalysis, and assessment of AEs, are standard evaluations to ensure subject safety.

- 9.5.4 Reporting of Serious Adverse Events, Pregnancy, and Events Associated with Special Situations
- 9.5.4.1 Reporting of Serious Adverse Events

All SERIOUS ADVERSE EVENTS, regardless of their relationship to study treatment, must be reported on a completed SAE form by email or fax as soon as possible but no later than 1 business day from the date the investigator becomes aware of the event.

All SERIOUS ADVERSE EVENTS, regardless of their relationship to study treatment, must be reported on a completed SAE form by email or fax as soon as possible but no later than 24 hours from when the investigator becomes aware of the event.

Serious adverse events, regardless of causality assessment, must be collected through the last visit and for 90 days after the subject's last dose or start day of another anticancer therapy, whichever is earlier. If the subject initiates new anticancer therapy within 30 days, then SAEs will be collected for 30 days following the last dose of E7766. All SAEs must be followed to resolution or, if resolution is unlikely, to stabilization. Any SAE judged by the investigator to be related to the study treatment or any protocol-required procedure should be reported to the sponsor regardless of the length of time that has passed since study completion.

The detailed contact information for reporting of SAEs is provided in the Investigator Study File.

**For urgent safety issues**, please ensure all appropriate medical care is administered to the subject and contact the appropriate study team member listed in the Investigator Study File.

It is very important that the SAE report form be filled out as completely as possible at the time of the initial report. This includes the investigator's assessment of causality.

Eisai Confidential Page 95 of 138

Any follow-up information received on SAEs should be forwarded within 1 business day of its receipt. If the follow-up information changes the investigator's assessment of causality, this should also be noted on the follow-up SAE form.

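### Protocol 9.5.4.2 fixes pregnancy reporting at 30 days after last treatment while contraception runs 180 days, so a subject whose follow-up ends early can fall into a gap of up to 150 days

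*Protocol*

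**What the plan says.** **Reporting.** Under Protocol Section 9.5.4.2, a pregnancy in a female subject or in a male subject's partner must be reported if the conception date "is either before the last visit or within 30 days of last study treatment". The two conditions are alternatives, so the later one governs. Exposure through breastfeeding has its own 30-day limit. The section also makes an adverse pregnancy outcome suspected to be drug related reportable without a time limit, and requires every pregnancy to be followed to outcome.

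**Contraception.** In Protocol Section 9.3.2, Criterion 13 requires women of childbearing potential to use contraception "throughout the entire study period and for 180 days after study drug discontinuation". Criterion 14 sets the same length for male subjects and their partners: "throughout the entire study period, and for 180 days after the last dose of study drug".

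**Visits after treatment.** Section 9.1.3.3 states: "An off-treatment assessment should occur within 30 days after the final dose of study treatment". Table 7 numbers that visit 98 and the Follow-Up Phase 100. Section 9.1.3.4 plans survival contacts every 12 weeks for up to 2 years, in person or by telephone. It also lets the sponsor close survival follow-up early. Under Table 7 footnote f, the last scheduled pregnancy test is at the off-treatment visit.

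**The concern.** The plan asks subjects to avoid pregnancy for 180 days, but the only fixed period in the reporting rule is 30 days. Beyond day 30 the duty to report rests on *last visit*, which is not defined at subject level and whose date depends on how long follow-up lasts. If follow-up stops before day 180, a pregnancy conceived while contraception is still required can fall outside the routine reporting rule, and so may not be followed to outcome.

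This is the first human study by the intratumoral route, and safety is a primary objective. A drug-related adverse outcome is easier to recognise if the pregnancy was already reported and followed.

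**Working it through.** The plan has no figure to reproduce; the check compares stated limits. Day 0 is the last dose. I treat drug discontinuation (Criterion 13) and last dose (Criterion 14) as the same day.

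**Inputs**

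| Item | Value | Source |
|---|---|---|
| Contraception period | 180 days | Protocol 9.3.2, Criteria 13 and 14 |
| Fixed reporting limit for conception | 30 days | Protocol 9.5.4.2 |
| Off-treatment visit | by day 30 | Protocol 9.1.3.3 |
| Follow-up contacts | every 12 weeks (84 days), up to 2 years | Protocol 9.1.3.4 |

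**Formula.** Let V be the day of the subject's last contact that counts as a visit. Then gap = max(0, 180 − max(30, V)).

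**Reading A: *last visit* means the off-treatment visit.** V is at most 30, so the gap is 180 − 30 = 150 days (days 31 to 180).

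**Reading B: *last visit* includes follow-up.** The protocol does not say when the 12-week clock starts, so two starting points are shown, ignoring the one-week window.

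| Last contact before follow-up ends | Clock from last dose | Clock from an off-treatment visit on day 30 |
|---|---|---|
| No follow-up contact | 180 − 30 = 150 | 180 − 30 = 150 |
| First | V = 84; 180 − 84 = 96 | V = 30 + 84 = 114; 180 − 114 = 66 |
| Second | V = 168; 180 − 168 = 12 | V = 30 + 168 = 198; gap 0 |
| Third | V = 252; gap 0 | gap 0 |

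**Which reading fits better?** Three things favour B:
- Table 7 gives follow-up its own visit number, after the off-treatment visit.
- The off-treatment visit is due by day 30, so under Reading A the first alternative would add almost nothing to the second.
- Section 5.1 defines the end of the study through "last subject/last visit, including discontinuation from the study for any reason". That is a study-level definition, but it uses the term for study exit.

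**Can follow-up end before day 180?** Yes. Under Section 9.1.3.4 it also stops at completion of the primary analysis, on withdrawal of consent, or if the sponsor ends it. As an illustration, SAP Section 5 places data cutoff after six months from the last subject's treatment start. If cutoff fell at exactly six months (taken as 182 days) and that subject's last dose was Cycle 1 Day 15 (14 days after the first), then 182 − 14 = 168 post-dose days would have passed. Longer-treated subjects would have fewer. The interval from cutoff to completion of the primary analysis is not stated, so this shows only that an early end is plausible.

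**The case against.** The strongest reply is that the rule is an either/or rule. On its natural reading, anyone still in follow-up at day 180 is fully covered. That stands, and it rules out a flat 150-day gap for every subject.

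A reader might also infer a conflicting 90-day limit, and so three competing limits. Section 9.5.1.5.2 says that "events associated with special situations include pregnancy or exposure to study drug through breastfeeding" and that "These events associated with special situations are to be captured using the SAE procedures", and Section 9.5.4.1 gives 90 days for SAEs. The documents do not support that inference:
- Section 9.5.1.5.2 goes on to treat special situations as SAEs only when they meet an SAE criterion. It can be read as saying how a pregnancy is captured, with Section 9.5.4.2 saying when it is reportable.
- The SAE rule reads "Serious adverse events, regardless of causality assessment, must be collected through the last visit and for 90 days". It contains the same undefined term, so a ceiling of 90 days is not established.

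Three further replies have weight:
- Important outcomes are largely covered. Section 9.5.4.2 classes congenital anomaly, perinatal death and abortion as SAEs, and Section 9.5.4.1 makes related SAEs reportable at any time. What remains is mainly late conceptions with normal or unrelated outcomes, and pregnancies nobody follows.
- Nothing in the documents says the reporting period must equal the contraception period. Matching them is a reviewer's standard, though the documents give no reason for 30 days.
- Where follow-up ends because consent is withdrawn, a longer limit would rarely help, since the site may never hear of the pregnancy. Early closure by the sponsor is the main case in which the change adds something.

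**Conclusion.** The point holds as a minor inconsistency in safety reporting. The gap is 0 days for subjects followed to day 180 and between 0 and 150 days for those whose follow-up ends sooner. The upper figure needs follow-up to end by about day 30, or a site to adopt the off-treatment reading. This rests on follow-up contacts, including telephone calls, counting as visits. Table 7 supports that, but no definition states it.

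Only the routine report of the pregnancy and its follow-up to outcome are at stake. Very few cases are expected: Protocol Section 9.3 planned about 35 to 40 escalation subjects, SAP Section 7 records that escalation ended early, and SAP Section 3.2.2 rules out expansion enrolment. The SAP does not say that follow-up was shortened. No endpoint or analysis is affected.

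**What to change.** In Protocol Section 9.5.4.2, for conception only, replace the 30-day limit after last study treatment with 180 days, matching Criteria 13 and 14. Leave the breastfeeding limit at 30 days. The meaning of *last visit* and the date follow-up closes would then no longer matter within the contraception period.

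The cost is one phrase, plus a few more pregnancy forms and outcome follow-ups, including for partners of male subjects. The change adds no scheduled question or test, so pregnancies arising after the off-treatment visit would still be reported only if the site learns of them.

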## 9.5.4.3 Reporting of Events Associated With Special Situations

9.5.4.3.1 REPORTING OF ADVERSE EVENTS ASSOCIATED WITH STUDY DRUG OVERDOSE, MISUSE, ABUSE, OR MEDICATION ERROR

Adverse events associated with study drug overdose, misuse, abuse, and medication error refer to AEs associated with uses of the study drug outside of that specified by the protocol. Overdose, misuse, abuse, and medication error are defined as follows:

Overdose Accidental or intentional use of the study drug in an amount higher

than the protocol-defined dose

Misuse Intentional and inappropriate use of study drug not in accordance with

the protocol

Abuse Sporadic or persistent intentional excessive use of study drug

accompanied by harmful physical or psychological effects

Medication error Any unintentional event that causes or leads to inappropriate study

drug use or subject harm while the study drug is in the control of site

personnel or the subject

All AEs associated with overdose, misuse, abuse, or medication error should be captured on the Adverse Event CRF and also reported using the procedures detailed in Reporting of Serious Adverse Events (Section 9.5.4.1) even if the AEs do not meet serious criteria. Abuse is always to be captured as an AE. If the AE associated with an overdose, misuse, abuse, or medication error does not meet serious criteria, it must still be reported using the SAE form and in an expedited manner but should be noted as nonserious on the SAE form and the Adverse Event CRF.

## 9.5.4.4 Expedited Reporting

The sponsor must inform investigators (or as regionally required, the head of the medical institution) and regulatory authorities of reportable events, in compliance with applicable regulatory requirements, on an expedited basis (ie, within specific time frames). For this reason, it is imperative that sites provide complete SAE information in the manner described above.

## 9.5.4.5 Breaking the Blind

Not applicable.

# 9.5.4.6 Regulatory Reporting of Adverse Events

Adverse events will be reported by the sponsor or a third party acting on behalf of the sponsor to regulatory authorities in compliance with local and regional law and established

Eisai Confidential Page 97 of 138

guidance. The format of these reports will be dictated by the local and regional requirements.

All studies that are conducted within any European country will comply with European Good Clinical Practice Directive 2005/28/EC and Clinical Trial Directive 2001/20/EC. All suspected unexpected serious adverse reactions (SUSARs) will be reported, as required, to the Competent Authorities of all involved European member states.

# 9.5.5 Completion/Discontinuation of Subjects

A subject may elect to discontinue the study at any time for any reason. All subjects who discontinue the study are to complete the study's early discontinuation procedures indicated in the Schedule of Procedures/Assessments (Table 7).

The investigator will promptly explain to the subject involved that the study will be discontinued for that subject and provide appropriate medical treatment and other necessary measures for the subject. A subject who has ceased to return for visits will be followed up by mail, phone, or other means to gather information such as the reason for failure to return, the status of treatment compliance, the presence or absence of AEs, and clinical courses of signs and symptoms.

Subjects who discontinue early from the study will be discontinued for 1 of these primary reasons: AE(s), lost to follow-up, subject choice, progression of disease, withdrawal of consent, pregnancy, study terminated by the sponsor, or other. In addition to the primary reason, the subject may indicate 1 or more secondary reason(s) for discontinuation. Study disposition information will be collected on the Subject Disposition CRF.

In the Dose Escalation part only, subjects who are not evaluable for DLT (eg, those subjects who fail to complete at least 2 E7766 injections during Cycle 1 for reasons other than DLT occurrence) should be replaced within their dose level, if at least 2 subjects in total have not been tested at the dose level.

